3.4. MTD Definition

The MTD is defined as the highest combination dose with a DLT rate <25% from the TITE-CRM model estimate (explained in [Section 9.2](#)).

3.5. Dose Expansion Test Dose

The Expansion Test Dose will be either the estimated MTD or a lower dose if emerging data suggest the estimated MTD is more toxic than originally believed.

3.6. Dose Expansion Phase

The Dose Expansion Phase will test PF-05082566 in combination with MK-3475 in patients with selected advanced solid tumor type to be determined based on emerging safety and clinical activity data from this study.

All patients in the Dose Expansion Phase may be enrolled simultaneously. The total number of patients enrolled into one or more Dose Expansion Phase cohorts will be determined based on the tumor type, and patient population emerging data from this study. PK samples will be collected from all evaluable patients in the Dose Expansion Phase Cohort.

Further experience in the Dose Expansion Phase Cohort may result in the need to explore a lower Expansion Test Dose. Only doses declared safe in the Dose Escalation Phase will be considered.

3.7. Recommended Phase 2 Dose

The RP2D is the dose of PF-05082566 and MK-3475 in combination chosen for further study based on Phase 1 results. If the MTD proves to be clinically feasible for long term administration in a reasonable number of patients, such dose usually becomes the RP2D. Once the MTD is estimated, additional patients may be enrolled at this dosing level. In the expansion cohort, patients' DLT data will be entered into the Bayesian statistical model of the TITE-CRM procedure. If the posterior distribution of the model incorporating the additional data from the expansion cohort suggests the estimated MTD is associated with a higher than expected DLT rate the next lower dose or an intermediate dose level will be expanded, and may be declared as the RP2D.

4. PATIENT SELECTION

This study can fulfill its objectives only if appropriate patients are enrolled. The following eligibility criteria are designed to select patients for whom protocol treatment is considered appropriate. All relevant medical and non-medical conditions should be taken into consideration when deciding whether this protocol is suitable for a particular patient.

Patient eligibility should be reviewed and documented by an appropriately qualified member of the investigator's study team before patients are included in the study.

4.1. Inclusion Criteria

Patients must meet all of the following inclusion criteria to be eligible for enrollment into the study:

1. Histological or cytological diagnosis of advanced/metastatic solid tumor malignancy which has progressed on standard therapy or for which no standard therapy is available.
2. Measurable disease per RECIST v1.1.
3. Expansion cohort patients must have tumor accessible for sequential biopsy (core needle biopsy or excision preferred).
4. Age 18 years or older.
5. Eastern Cooperative Oncology Group (ECOG) performance status of 0 or 1 (see [Appendix 2](#)).
6. Adequate bone marrow function, defined as absolute neutrophil count (ANC) $\geq 1.5 \times 10^9/L$ ($\geq 1,500/\mu L$), platelet count $\geq 100 \times 10^9/L$ ($\geq 100,000/\mu L$), and hemoglobin $> 9.0 \text{ g/dL}$ ($> 5.6 \text{ mmol/L}$). Patients must be transfusion independent (ie, no blood product transfusions for a period of at least 14 days prior to study registration).
7. Adequate renal function, including serum creatinine $\leq 1.5 \times$ upper limit of normal (ULN) or estimated creatinine clearance $\geq 60 \text{ mL/min}$ as calculated using the method standard for the institution.
8. Adequate liver function, including: Total serum bilirubin $\leq 1.5 \times$ ULN (unless the patient has documented Gilbert syndrome), Aspartate and Alanine Aminotransferase (AST and ALT) $\leq 2.0 \times$ ULN, Alkaline phosphatase $\leq 2.5 \times$ ULN; ($\leq 5 \times$ ULN in case of bone metastasis).
9. Resolved acute effects of any prior therapy to baseline severity or Grade ≤ 1 CTCAE except for AEs not constituting a safety risk by investigator judgment.
10. Serum/urine pregnancy test (for females of childbearing potential) negative at screening and at the baseline visit (before the patient may receive the investigational product).
11. Male and female patients of childbearing potential must agree to use two (2) highly effective methods of contraception throughout the study and for 120 days after the last dose of assigned treatment.

Female patients who are not of childbearing potential (ie, meet at least one of the following criteria):

- Have undergone a documented hysterectomy and/or bilateral oophorectomy;
 - Have medically confirmed ovarian failure or;
 - Achieved post-menopausal status, defined as follows: cessation of regular menses for at least 12 consecutive months with no alternative pathological or physiological cause; and have a serum follicle stimulating hormone (FSH) level within the laboratory's reference range for postmenopausal women.
12. Evidence of a personally signed and dated informed consent document indicating that the patient has been informed of all pertinent aspects of the study.
13. Patients who are willing and able to comply with scheduled visits, treatment plans, laboratory tests and other procedures.

4.2. Exclusion Criteria

Patients presenting with any of the following will not be included in the study:

1. CNS primary malignancies, active seizure disorder or spinal cord compression, or carcinomatous meningitis. Patients with previously treated brain metastases may participate provided they are stable (without evidence of progression by imaging for at least four weeks prior to registration and any neurologic symptoms have returned to baseline), have no evidence of new or progressing brain metastases, have not used steroids for at least 14 days prior to study entry. This exception does not include carcinomatous meningitis which is excluded regardless of clinical stability.
2. Chemotherapy, growth factors or investigational agents within 28 days before registration.
3. Systemic steroid therapy or any other form of immunosuppressive therapy within 14 days prior to registration.
4. Radiation therapy within 14 days of study entry. Therapeutic or experimental monoclonal antibodies in last 60 days prior to registration.
5. Therapeutic or experimental monoclonal antibodies in last 60 days prior to registration.
6. History of any of the following toxicities associated with a prior immunotherapy:
 - Grade ≥ 3 immune-mediated adverse event that was considered related to previous immunotherapy and required immune suppressive therapy;
 - Grade ≥ 2 hepatic function-related adverse event that persisted more than 1 week, was considered related to immunotherapy, or required treatment discontinuation or immunosuppressive therapy (previous immunotherapies include any anti-CD137, an anti-Programmed death-1 (anti-PD-1), anti-Programmed death

ligand 1 (anti-PD-L1), anti-Programmed death ligand 2 (anti-PD-L2), or anti-Cytotoxic T lymphocyte-associated antigen 4 (anti-CTLA-4) antibody, or any other antibody or drug specifically targeting T-cell costimulation or checkpoint pathways).

7. Major surgery within 28 days of registration.
8. History of active ethanol abuse, hepatitis (eg, alcohol or non-alcohol steatohepatitis [NASH], drug related, auto-immune, virally related), or liver lesions greater than 4 cm on the longest axis.
9. Has received a live vaccine within 30 days prior to registration.
10. Active and clinically significant bacterial, fungal or viral infection including hepatitis B (HBV), hepatitis C (HCV), known human immunodeficiency virus (HIV) or acquired immunodeficiency syndrome (AIDS)-related illness (HIV testing is not required), including patients who have an active infection requiring systemic therapy.
11. Any of the following within the 12 months prior to registration: myocardial infarction, uncontrolled angina, coronary/peripheral artery bypass graft, symptomatic congestive heart failure, cerebrovascular accident or transient ischemic attack and 6 months for deep vein thrombosis or pulmonary embolism.
12. Diagnosis of any other malignancy within 2 years prior to registration, except for adequately treated basal cell or squamous cell skin cancer, or carcinoma in situ of the breast or of the cervix.
13. Pregnant females; breastfeeding females; male patients with partners currently pregnant; male and female patients of childbearing potential who are unwilling or unable to use two (2) highly effective methods of contraception as outlined in this protocol for the duration of the study and for 120 days after last dose of investigational product.
14. Known prior or suspected hypersensitivity to study drugs or any component in their formulations.
15. Patients who previously had a severe hypersensitivity reaction to treatment with another monoclonal antibody or who are known to be positive for anti-drug antibodies (ADA) to MK-3475 or PF-05082566.
16. Other severe acute or chronic medical or psychiatric condition, including recent (within the past year) or active suicidal ideation or behavior, or laboratory abnormality that may increase the risk associated with study participation or investigational product administration or may interfere with the interpretation of study results and, in the judgment of the investigator, would make the patient inappropriate for entry into this study.

17. History of or known presence of extensive, disseminated/bilateral or Grade 3 or 4 interstitial fibrosis or interstitial lung disease, including a history of pneumonitis, hypersensitivity pneumonitis, interstitial pneumonia, interstitial lung disease, obliterative bronchiolitis, or pulmonary fibrosis, but not including a history of prior radiation pneumonitis. Patients with clinically significant lung disease requiring oxygen therapy (eg, COPD).
18. Active autoimmune disease or a documented history of autoimmune disease or syndrome that requires systemic steroids or immunosuppressive agents. Patients with vitiligo or resolved childhood asthma/atopy would be an exception. Patients that require intermittent use of bronchodilators, inhaled steroids, or local steroid injections and patients with hypothyroidism stable on hormone replacement will not be excluded from the study.
19. Participation in other studies within 4 weeks before the current study begins and/or during study participation.
20. Patients who are investigational site staff members directly involved in the conduct of the study and their family members, site staff members otherwise supervised by the investigator, or patients who are Pfizer employees directly involved in the conduct of the study.

4.3. Life Style Guidelines

4.3.1. Contraception

In this study, patients of childbearing potential will receive PF-05082566 and MK-3475, agents for which the teratogenic risk is currently unknown. Two (2) methods of highly effective contraception must be used throughout the study and continued for at least 120 days after the last dose. The investigator or his/her designee, in consultation with the patient, will select the most appropriate methods of contraception for the individual patient from the permitted list of contraception methods (see below), and instruct the patient in their consistent and correct use. Patients need to affirm that they meet at least 2 of the selected methods of contraception. The investigator or his/her designee will discuss with the patient the need to use highly effective contraception consistently and correctly according to [Table 2](#) Schedule of Activities (SOA) and document such conversation in the patient chart. In addition, the investigator will instruct the patient to call immediately if the selected birth control method is discontinued or if pregnancy is known or suspected.

Highly effective methods of contraception are those that, alone or in combination, result in a failure rate of less than 1% per year when used consistently and correctly (ie, perfect use) and include:

1. Established use of oral, inserted, injected or implanted hormonal methods of contraception is allowed provided the patient remains on the same treatment throughout the entire study and has been using that hormonal contraceptive for an adequate period of time to ensure effectiveness.

2. Correctly placed copper containing intrauterine device (IUD).
3. Male condom or female condom used WITH a spermicide (ie, foam, gel, film, cream, suppository).
4. Male sterilization with absence of sperm in the post-vasectomy ejaculate.
5. Bilateral tubal ligation or bilateral salpingectomy or bilateral tubal occlusive procedure (provided that occlusion has been confirmed in accordance with the device's label).

4.4. Sponsor Qualified Medical Personnel

The contact information for the sponsor's appropriately qualified medical personnel for the trial is documented in the study contact list located in the study manual (coordinator's manual).

To facilitate access to appropriately qualified medical personnel on study related medical questions or problems, patients are provided with a contact card. The contact card contains, at a minimum, protocol and investigational compound identifiers, patient study number, contact information for the investigational site and contact details for a help desk in the event that the investigational site staff cannot be reached to provide advice on a medical question or problem originating from another healthcare professional not involved in the patient's participation in the study. The help desk number can also be used by investigational staff if they are seeking advice on medical questions or problems, however it should only be used in the event that the established communication pathways between the investigational site and the study team are not available. It is therefore intended to augment, but not replace the established communication pathways between the investigational site and study team for advice on medical questions or problems that may arise during the study. The help desk number is not intended for use by the patient directly, and if a patient calls that number, he or she will be directed back to the investigational site.

5. STUDY TREATMENTS

5.1. Allocation to Treatment

Dose level allocation will be performed by the Sponsor after patients have given their written informed consent and have completed the necessary baseline assessments. The site staff will fax or email a complete Registration Form to the designated Sponsor study team member. The Sponsor will assign a patient identification number, which will be used on all Case Report Form (CRF) pages and other trial-related documentation or correspondence referencing that patient and (email) to the site.

For the purposes of this protocol, study drug refers to both PF-05082566 and MK-3475. No patient shall receive study drug until the Investigator or designee has received the following information in writing from the Sponsor:

- Confirmation of the patient's enrollment;

- Specification of the dose level for that patient;
- Permission to proceed with dosing the patient.

The Sponsor or designee will notify the other sites of the inclusion of a new patient, and will inform study sites about the next possible enrollment date.

5.2. Drug Supplies

PF-05082566 and MK-3475 will be supplied for the study by Pfizer Global Clinical Supply, Worldwide Research and Development. Drug supplies will be shipped to the study sites with a Drug Shipment & Proof of Receipt form. This form should be completed, filed, and the shipment confirmed as directed on the bottom of the Drug Shipment & Proof of Receipt form.

5.2.1. Dosage Form and Packaging

5.2.1.1. PF-05082566

PF-0508256 drug product will be supplied in glass vials at a 10 mg/mL concentration and labeled as open supplies. Each vial is packed in an individual carton.

5.2.1.2. MK-3475

MK-3475 will be supplied in single-use vials containing 100 mg/4mL sterile solution for intravenous administration. Each vial is sealed with a coated stopper and oversealed and labeled according to local regulatory requirements.

5.2.2. Preparation and Dispensing

The site will complete required dosage Preparation Record located in the study manual. The use of the Preparation Record is preferred but it does not preclude the use of an existing appropriate clinical site documentation system. The existing clinical site's documentation system should capture all pertinent/required information on the preparation and administration of the dose. This may be used in place of the Preparation Record after approval from the Pfizer monitor.

See the Dosage and Administration Instructions (DAI) form for instructions on how to prepare the investigational product for administration. Investigational product should be prepared and dispensed by an appropriately qualified and experienced member of the study staff (eg, physician, nurse, physician's assistant, practitioner, pharmacist, or medical assistant) as allowed by local, state, and institutional guidance.

5.3. Administration

A cycle is defined as the time from Day 1 dose to the next Day 1 dose of PF-05082566. If there are no treatment delays, a cycle will be 3 weeks in duration.

All trial treatments will be administered on an outpatient basis. After Cycle 1, study drugs may be administered up to 2 days before or after the scheduled treatment day of each cycle

for administrative reasons. Patients will be observed in the clinic for at least 2 hours after each infusion of study drug.

All patients should be weighed within 72 hours prior to dosing for every cycle to ensure they did not experience either a weight loss or gain >10% from the prior weight used to calculate the amount of study drug required for dose preparation. Decision to recalculate the study drug dose based on the weight obtained at each cycle can be in accordance with institutional practice, however if the patient experienced either a weight loss or gain >10% compared to the weight used to calculate the initial dose, the amount of study drug required for preparation and administration for the current cycle must be recalculated using this most recent weight obtained.

The study drug dose escalation levels are shown in [Table 1](#). In addition, doses of PF-05082566 and MK-3475 available for dose modification according to guidelines in [Section 5.3.7](#), are shown below in [Table 7](#).

5.3.1. PF-05082566

PF-05082566 will be administered intravenously (IV), q3wks on Day 1 of each cycle.

PF-0508256 will be administered as a 1 hour infusion. The infusion rate should be reduced or interrupted in the case of symptoms of infusion reaction, and symptomatic treatment administered. The infusion may be continued at one-half the previous rate upon improvement of symptoms. If symptoms persist or worsen, the infusion should be discontinued.

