5.3.2. MK-3475

MK-3475 will be administered IV, q3wks on Day 1 of each cycle, 30 minutes after completion of the PF-05082566 infusion and after the post-PF-05082566 and/or pre-MK-3475 pharmacokinetic blood samples are drawn.

MK-3475 will be administered as a 30 minute IV infusion. Sites should make every effort to target infusion timing to be as close to 30 minutes as possible. The exact duration of infusion should be recorded in both source document and CRFs. The infusion rate should be reduced or interrupted in the case of symptoms of infusion reaction, and symptomatic treatment administered. The infusion may be continued at one-half the previous rate upon improvement of symptoms. If symptoms persist or worsen, the infusion should be discontinued.

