5.7.2. Supportive Care Guidelines For Infusion Reactions to Either Study Drug

Acute infusion reactions (which can include cytokine release syndrome, angioedema, or anaphylaxis) are different from allergic/hypersensitive reactions, although some of the manifestations are common to both AEs. Signs and symptoms usually develop during or shortly after drug infusion and generally resolve completely within 24 hours of completion of infusion. Signs/symptoms may include: Allergic reaction/hypersensitivity (including drug fever); Arthralgia (joint pain); Bronchospasm; Cough; Dizziness; Dyspnea (shortness of breath); Fatigue (asthenia, lethargy, malaise); Headache; Hypertension; Hypotension; Myalgia (muscle pain); Nausea; Pruritis/itching; Rash/desquamation; Rigors/chills; Sweating (diaphoresis); Tachycardia; Tumor pain (onset or exacerbation of tumor pain due to treatment); Urticaria (hives, welts, wheals); and Vomiting.

[Table 12](#) below shows treatment guidelines for patients who experience an infusion reaction associated with administration of either study drug.

In the event that a site does not have established procedures for the treatment of study drug associated infusion reactions, the following guidelines are provided in [Table 12](#).

Table 12. Infusion Reaction Treatment Guidelines for Either Study Drug

NCI CTCAE Grade	Treatment	Premedication at subsequent dosing
Grade 1 Mild reaction; infusion interruption not indicated; intervention not indicated	Increase monitoring of vital signs as medically indicated until the patient is deemed medically stable in the opinion of the investigator.	None

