Grade 2 Requires infusion interruption but responds promptly to symptomatic treatment (eg, antihistamines, NSAID, narcotics, IV fluids); prophylactic medications indicated for <= 24 hours	
Stop Infusion and monitor symptoms. Additional appropriate medical therapy may include but is not limited to:
 
 IV fluid Antihistamines NSAIDS Acetaminophen Narcotics 
Increase monitoring of vital signs as medically indicated until the patient is deemed medically stable in the opinion of the investigator. If symptoms resolve within one hour of stopping drug infusion, the infusion may be restarted at 50% of the infusion rate (eg, from 100 mL/hr to 50 mL/hr). Otherwise dosing will be held until symptoms resolve and the patient should be premedicated for the next scheduled dose. Patients who develop Grade 2 toxicity despite adequate premedication should be permanently discontinued from further trial treatment administration.
	
Patients may be premedicated 1.5 h (\pm30 minutes) prior to infusion of PF-05082566 and MK-3475) with:
 
Diphenhydramine 50 mg PO (or equivalent dose of antihistamine).
 
Acetaminophen 500-1000 mg po (or equivalent dose of antipyretic).

Grades 3 or 4 Grade 3; Prolonged (ie, not rapidly responsive to symptomatic medication and/or brief interruption of infusion); recurrence of symptoms following initial improvement; hospitalization indicated for other clinical sequelae (eg, renal impairment, pulmonary infiltrates) Grade 4: Life-threatening; pressor of ventilatory support indicated	
Stop infusion. Additional appropriate medical therapy may include but is not limited to:
 
 IV fluids Antihistamines NSAIDS Acetaminophen Narcotics Oxygen Pressors Corticosteroids Epinephrine 
Increase monitoring of vital signs as medically indicated until the patient is deemed medically stable in the opinion of the investigator. Hospitalization may be indicated. Patient is permanently discontinued from further trial treatment administration.
	No subsequent dosing
Appropriate resuscitation equipment should be available in the room and a physician readily available during the period of drug administration For further information, please refer to the Common Terminology Criteria for Adverse Events v4.03 (CTCAE) at http://ctep.cancer.gov		

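### Sections 5.3.1 and 5.3.2 let an infusion continue at half rate once a reaction improves, without tying this to Table 12, which is stricter in three cases

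*Protocol*

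**What the plan says.** Section 5.3.1 (PF-05082566) and Section 5.3.2 (MK-3475) carry the same instruction. If reaction symptoms appear, the rate is reduced or the infusion interrupted and symptoms are treated. Then "The infusion may be continued at one-half the previous rate upon improvement of symptoms". The only stop rule is "If symptoms persist or worsen, the infusion should be discontinued", and it ends that infusion, not trial treatment. Neither section mentions CTCAE grade, elapsed time or Table 12.

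Table 12 in Section 5.7.2 is graded:

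- **Grade 2.** The infusion is stopped. "If symptoms resolve within one hour of stopping drug infusion, the infusion may be restarted at 50% of the infusion rate"; otherwise dosing is held and the next dose should be premedicated. In addition, "Patients who develop Grade 2 toxicity despite adequate premedication should be permanently discontinued from further trial treatment administration".
- **Grade 3 or 4.** The infusion is stopped and there is no later dosing: "Patient is permanently discontinued from further trial treatment administration".

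Two places bear on the status of Table 12. The notes under Table 8 refer readers to it for dose modification after infusion reactions. Section 5.7.2 first presents it as the guideline for reactions to either drug, then introduces it with a condition: "In the event that a site does not have established procedures for the treatment of study drug associated infusion reactions".

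**The concern.** Staff managing a reaction need a single answer on whether the drug may be restarted. A reader who opens the administration sections finds a permission that depends only on improvement. A reader who opens Table 12 finds limits by grade and time, and in some cases the end of treatment. Nothing in Sections 5.3.1 or 5.3.2 tells the first reader that those limits exist.

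The direct consequence is re-exposure of a patient whom another part of the same protocol would hold or take off treatment. In a multi-center study, similar reactions could also be handled differently from site to site. Section 1.2.7 states that no nonclinical toxicology studies were done with these two agents together, so clear restart limits are worth having.

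**Working it through.** No arithmetic applies, so the check sets the rules side by side.

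| Reaction | Sections 5.3.1 / 5.3.2 | Table 12 |
|---|---|---|
| Grade 2, resolved within one hour | Half rate allowed | Half rate allowed |
| Grade 2, improved but not resolved within one hour | Half rate allowed | Dosing held |
| Grade 2 in an adequately premedicated patient, then improved | Half rate allowed | Permanent discontinuation |
| Grade 3 or 4, then improved | Half rate allowed as written | Permanent discontinuation, no later dosing |
| Grade 3 or 4, not improving or getting worse | That infusion stopped | Infusion stopped, permanent discontinuation |

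Rows two to four are the conflict. In row five both texts stop the infusion, so there is no conflict over a same-day restart.

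**How wide is row four?** Table 12's Grade 3 covers reactions slow to respond to medication or a short pause, and reactions that return after early improvement. Most of these would also meet the stop rule in 5.3.1. What remains is mainly a Grade 3 reaction graded on the need for hospital admission, or a Grade 4 reaction, that then improves. That is uncommon, but the text does not exclude it.

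**Do the general rules close the gap?** Section 5.3.6 bars re-treatment after an interruption for related toxicity until non-hematologic events are back to baseline or Grade 1, or Grade 2 at the investigator's discretion. It then lets both drugs resume, and asks only that discontinuation be considered for severe or life-threatening events. Table 8 holds Grade 3 and 4 non-hematologic events and allows restart one dose level lower, although its own notes refer infusion reactions to Table 12. These rules narrow the gap. They do not reproduce the permanent discontinuation that Table 12 requires in rows three and four.

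**Does it reach the primary endpoint?** Attributable non-laboratory Grade 3 or 4 reactions are DLTs under Section 3.3 whichever text a site follows. Status could differ only through a Grade 2 reaction that leaves an infusion ungiven, because failure to complete two infusions of both drugs in the observation period is itself a DLT criterion. The clearest route is a Grade 2 reaction in Cycle 1, then premedication, then another Grade 2 reaction during the Cycle 2 PF-05082566 infusion. MK-3475 starts "30 minutes after completion of the PF-05082566 infusion", so under Table 12 the second MK-3475 infusion would not be given, whereas under 5.3.1 both could be completed. This needs that whole sequence and also a site that follows 5.3.1 instead of Table 12.

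**Can the size be estimated?** No. The documents give no infusion-reaction rate for the combination. Table 6 lists no infusion reaction. It covers 23 single-agent patients at 0.006 to 0.24 mg/kg, all below the 0.45 mg/kg starting dose and without MK-3475. The Protocol Summary reports single-agent tolerability up to 2.4 mg/kg but gives no patient count.

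**The case against.** The best reply is that the texts can be read together. Sections 5.3.1 and 5.3.2 are short administration paragraphs giving a permission, and Table 12 is the specific rule that limits it by grade. Section 5.7.2 and the Table 8 notes both direct infusion reactions to Table 12, and a site that follows Table 12 breaches nothing in 5.3.1 or 5.3.2. This largely stands. A reader might infer that the protocol gives no guidance at all on which text to use; those two pointers show otherwise. What the reply does not remove is that the sections a site consults for giving the drug lack the cross-reference. The condition in 5.7.2 also lets a site with its own procedures read the discontinuation rules as not binding on it.

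A second reply is that premedication is part of the safeguard. The premedication column says "Patients may be premedicated 1.5 h", which alone makes it look optional. The Grade 2 treatment cell goes further and says the patient should be premedicated if the reaction outlasts one hour. That is correct, and it means Table 12 is not lax on premedication. It does not affect the half-rate permission elsewhere.

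A third reply is that deferring to local procedures is a deliberate choice. For treating the reaction, and arguably for Grade 2 handling in general, that is reasonable. It is harder to defend as a way around permanent discontinuation after Grade 3 or 4.

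**Conclusion.** The inconsistency is real and worth correcting. As written, the administration sections permit half-rate continuation in three situations where Table 12 holds dosing or ends treatment. Two are Grade 2 situations; the third, an improving Grade 3 or 4 reaction, is uncommon. The consequence is for patient safety and consistency between sites, and it is partly mitigated by the stop rule in 5.3.1 and 5.3.2, by Section 5.3.6 and by the pointers to Table 12.

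Two stronger readings are not supported. A reader might infer that severe reactions would routinely be re-infused; the overlap between Table 12's Grade 3 definition and the stop rule argues against that. A reader might also infer that DLT counts, and through them the maximum tolerated dose, would be distorted; that depends on a remote Grade 2 sequence, and the documents supply no rate for it. No magnitude is claimed. The conclusion rests only on the wording of the sections compared.

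**What to change.** 1. In Sections 5.3.1 and 5.3.2, make half-rate continuation subject to Table 12: for Grade 2, only if symptoms resolve within one hour; no restart after Grade 3 or 4, or after Grade 2 in an adequately premedicated patient.
2. In Section 5.7.2, state that deference to site procedures covers treatment of the reaction and does not override permanent discontinuation after Grade 3 or 4.

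I would not go on to make all of Table 12 a mandatory minimum at every site. For Grade 2 that would undo the deference the protocol chose, and the case for it is debatable.

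Optional: cite Table 12 in Schedule of Activities footnote 18, which now sends readers to Section 5.3.6, where there is no rule specific to infusion reactions; and say in Section 3.3 whether an infusion stopped or not given under Table 12 for a Grade 2 reaction counts as failure to complete two infusions.

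The cost is a few sentences in three sections, with no new procedures, patients or analyses. Sites lose a little discretion, and a few patients will lose the remainder of an infusion or stop treatment, which Table 12 already prescribes.
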